2.2. SPECIFIC AIMS

Specific aim #1 - Efficacy: To determine the acute changes in oxygenation and echocardiography during treatment with IV milrinone (improvement in OI/OSI and PaO₂ at 24 hours from baseline and changes in right ventricular pressure and function at 24 – 72 h from baseline)

Specific aim #2 - Safety: To determine the safety of IV milrinone treatment by comparing the incidence of serious adverse events (severe hypotension, bleeding - intracranial and extracranial hemorrhage and arrhythmias).

Specific aim #3 - Outcome: To determine the infant's status (pulmonary and nutritional) at discharge and conduct a series of telephonic surveys at 4, 8 and 12 months of postnatal age to assess the impact of baseline characteristics (gender, gestational age at birth, mode of delivery, birth weight, time of diagnosis – antenatal vs. postnatal), study intervention and other therapies and interventions on infant's status.

Specific aim #4 - Feasibility: To derive preliminary estimates of the incidence of survival without ECMO in the control and IV milrinone treatment groups and to demonstrate the feasibility of conducting a large randomized controlled clinical trial.

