2.3. BACKGROUND

2.3.1. Congenital Diaphragmatic Hernia

Congenital diaphragmatic hernia (CDH) is one of the common serious congenital anomalies managed in the neonatal intensive care unit (NICU) (Yoder, Lally et al. 2012). Despite many technological advances over the past two decades, including high frequency ventilation, iNO, surfactant replacement therapy and ECMO, CDH presenting in the neonatal period continues to be associated with relatively high rates of morbidity and mortality (28-30%)(Keller 2012, Yoder, Lally et al. 2012) (Table 1). Survival of infants at tertiary care centers automatically selects for patients who survive birth, resuscitation, and transport from an outside facility, and therefore likely underestimates the true hidden mortality associated with CDH. The major underlying pathophysiology in such infants appears to be a combination of lung immaturity, hypoplasia, and persistent pulmonary hypertension of the newborn (PPHN), which may be further

aggravated by left ventricular underdevelopment (Schwartz, Vermilion et al. 1994, Irish, Karamanoukian et al. 1996, Aggarwal, Stockman et al. 2011, Menon, Tani et al. 2012) (figure 1). Between 7/2008 and 6/2013, CDH was the diagnosis associated with the highest mortality among patients requiring ECMO for neonatal respiratory indications (table 1 and 2). Infants with CDH have prolonged length of stay in the NICU compared to many other congenital anomalies including critical congenital heart defects (table 1).

Table 1. Survival and length of stay for babies with CDH and severe congenital heart disease cared in hospitals affiliated with Children's Hospital Neonatal Database (CHND) between June 2010 and March 2013

Condition	Discharge outcome	Number	Average length of stay	Median length of stay
Congenital diaphragmatic hernia (CDH)	Survival	341 (68%)	52 d	37 d
	Death	160 (32%)	22 d	16 d
Congenital heart disease (life threatening)	Survival	94 (73%)	24 d	16.5 d
	Death	35 (27%)	14 d	7 d

Table 2. Neonatal Respiratory ECMO Runs by Diagnosis (July 2008 – June 2013)
Data from ELSO registry – date of access July 01, 2013

Diagnosis	Total Runs (% total)	Survived	% Survived
Congenital diaphragmatic hernia (CDH)	1263 (29.8%)	625	49.5%
Meconium aspiration syndrome (MAS)	1069 (25.3%)	1002	93.7%
Persistent pulmonary hypertension of the newborn (PPHN/PFC)	896 (21.1%)	677	75.6%
Respiratory distress syndrome (RDS)	80 (1.9%)	65	81.3%
Sepsis	248 (5.9%)	141	56.9%
Pneumonia	53 (1.3%)	29	54.7%

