Air-leak syndrome	11 (0.3%)	7	63.6%
Others	612 (14.4%)	329	53.8%
Total	4232	2875	67.9%

In spite of such high mortality, only two randomized controlled trials (NINOS CDH pilot) targeting treatment of PPHN associated with CDH with iNO has been published to date (1997). This study failed to demonstrate any benefit of iNO; in fact, the need for ECMO was significantly increased in iNO treated infants. A second trial (VICI) evaluating high frequency oscillation vs.

conventional ventilation in Europe was published in 2016 (table 3) (Snoek, Capolupo et al. 2014) (Snoek, Capolupo et al. 2016). The overall mortality by one year of postnatal age was 27% in this trial. This trial showed some benefits in the conventional ventilation arm compared to HFV but was stopped prior to completion of the expected sample size.

Table 3. Morbidity and mortality in CDH associated with initial mode of ventilation (VICI trial) (Snoek, Capolupo et al. 2014) (Snoek, Capolupo et al. 2016)

Variables: corrected for center (results are presented as n (%) or median (IQR)	HFO (n = 80)	CMV (n = 91)	p-value
Length of ventilation (days)	13 (8–23)	10 (6–18)	0.03
Severity CLD			
No CLD	37 (46.3%)	50 (54.9%)	
Mild CLD	7 (8.8%)	13 (14.3%)	
Moderate CLD	2 (2.5%)	1 (1.1%)	
Severe CLD	9 (11.3%)	6 (6.6%)	
Died	25 (31.3%)	21 (23.1%)	0.13
ECMO (in ECMO centers only)	24 (51.1%)	16 (26.2%)	0.007
Inhaled nitric oxide	45 (56.3%)	39 (42.9%)	0.045
Sildenafil	25 (31.3%)	11 (12.1%)	0.004
Inotropics	73 (91.3%)	73 (80.2%)	0.08
Duration inotropics (days) (in survivors only)	8 (4.25- 19)	6 (3.25- 11.75)	0.02
Presence of pulmonary hypertension	57 (71.3%)	59 (65%)	0.16
Severity of pulmonary hypertension			
None	20 (25%)	29 (31.9%)	
< 2/3 systemic	9 (11.3%)	10 (11%)	
2/3 systemic – systemic	26 (32.5%)	26 (28.6%)	
> systemic	22 (27.5%)	21 (23%)	
Missing	3	5	
Switch to CMV	24		
Switch to HFV		14	
Treatment failures (hypoxemia or hypercarbia or hypotension or OI>40 or increase in inspiratory pressure	27 (33.3%)	20 (22%)	0.01

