3.1. PRIMARY OUTCOME

The primary outcome is the oxygenation response, as determined by change in OI (or OSI if no arterial blood gas is available) at 24h after initiation of study drug. In patients that require ECMO or die prior to completion of 24h from the initiation of the study drug, the last OI (or OSI, if no arterial blood gas is available) prior to initiation of ECMO or death will be used for analysis. A difference in OI of 4 points in mean change from baseline OI at 24 h between experimental and control groups will be considered significant (OI increased by 4 ± 14.8 in the control group and decreased by 2.7 ± 23.4 following iNO in the CDH NINOS study (1997). In the Patel study, following milrinone infusion, OI decreased by 2.7 ± 1.7 from baseline by 12-24 h and 5.5 ± 3.2 by 48-72 h; the mean change in OI of both these time points is a decrease by 4.1 ± 1.5 (Patel 2012)). This outcome will be used for sample size calculation. Although a decrease in OI by 4 points may not be clinically significant, this number is based on the only published case series showing the use of milrinone in CDH. In patients without an arterial line (or if the line is lost), oxygen saturation index (OSI) will be calculated using a preductal oximeter. (Rawat, Chandrasekharan et al. 2015)

Oxygenation index (OI) = Mean airway pressure (cm H₂O) x FIO₂ x 100 ÷ PaO₂ (mm Hg)

Oxygen saturation index (OSI) = Mean airway pressure (cm H₂O) x FIO₂ x 100 ÷ SpO₂ (%)

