3.5. POTENTIAL RISKS AND BENEFITS TO SUBJECTS

Infants with CDH represent a high-risk population with mortality ranging from 30 to 40%. Additional risks from the use of IV milrinone include systemic hypotension, intracranial hemorrhage (reported in critically ill neonates with PPHN) and arrhythmias (reported in adults). The anticipated benefit is improvement in oxygenation and reduced need for ECMO.

Systemic hypotension is commonly seen in patients with CDH. In recent studies 80-90% of patients with CDH required treatment with vasoactive medications. (Snoek, Capolupo et al. 2016) Patients will be closely monitored for systemic hypotension due to its association with increased right –to-left shunting and hypoxemia. Study drug will be discontinued in the presence of 'severe' or 'life-threatening' systemic hypotension as outlined in the MOP that cannot be explained by other causes (such as sepsis or pneumothorax) and described below.

- a. Severe hypotension:
 - decrement in mean BP > 20 to 30 mmHg compared to the most recent value during the period prior to study drug or at baseline OR
 - receiving extensive volume therapy (40 to 80 ml/kg during a 24-hour period of the study monitoring period: onset of study drug to 24 hours after discontinuation of study drug) OR
 - escalation of vasoactive inotrope score by 20 to 30 compared to the score at baseline
- b. Life-threatening hypotension:
 - Decrease in mean BP > 30 mmHg compared to the most recent value during the period prior to study drug or at baseline OR
 - receiving volume therapy (> 80 ml/kg during a 24-hour period of the study monitoring period: onset of study drug to 24 hours after discontinuation of study drug) OR
 - escalation of vasoactive inotrope score by > 30 compared to the score at baseline)

(i) Vasoactive inotrope score calculation (vasoactive inotrope score = dopamine dose ($\mu\text{g}/\text{kg}/\text{min}$) + dobutamine dose ($\mu\text{g}/\text{kg}/\text{min}$) + epinephrine dose ($\mu\text{g}/\text{kg}/\text{min} \times 100$) + norepinephrine dose ($\mu\text{g}/\text{kg}/\text{min} \times 100$) + phenylephrine dose ($\mu\text{g}/\text{kg}/\text{min} \times 100$) + vasopressin dose ($\text{U}/\text{kg}/\text{min} \times 10000$) (Gaies, Gurney et al. 2010)

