5.4 STATISTICAL ANALYSIS PLAN

Baseline data will be collected prior to randomization including gestational age, side of the diaphragmatic hernia, birth weight, mode of delivery and arterial blood gas parameters (oxygenation index-OI) and/or pulse oximetry data (oxygen saturation index-OSI). Data from a baseline clinical echocardiogram is recorded (if performed prior to study drug initiation or within 2h of initiation of study drug). During the infusion of study drug, arterial blood gas parameters and hemodynamic data (blood pressure, heart rate and echocardiography results) will be recorded. After completing the study infusion, surgical details, and mortality information will be collected. Among survivors, respiratory and nutritional status at discharge and at 4, 8 and 12 months of age will be collected.

Data will be presented as mean \pm SD for normally distributed variables and as median and ranges (with percentiles) for non-normally distributed data. All analysis will be by intention-to-treat. Baseline characteristics will be compared between treatment groups using chi-square and Fisher's exact test for discrete variables and t-test and ANOVA for continuous variables. The primary outcome, difference from baseline OI at 24 h, will be compared between treatment groups using a general linear model adjusted for the stratification factor of HRF severity. Other continuous outcomes will be analyzed similarly. Models for longitudinal outcomes such as oxygenation and vasoactive inotrope scores (short-term) and nutritional and pulmonary outcomes at 12 months (long-term) will include the effect of time, the interaction between time and treatment, and random effects to account for the correlation between measures taken on the same individual over time. Categorical outcomes will be analyzed using analogous generalized linear models. Cox regression models (with adjustment for HRF severity) will be used to plot proportion of responders who survive without ECMO against survival time in hours. Analyses may adjust for clinical site if treatment assignments are severely imbalanced for some sites provided that it is computationally feasible to do so. The potential influence of baseline measures such as time of diagnosis – antenatal vs. postnatal, side of the defect, and gender on pulmonary and nutritional outcome will be explored through the use of additional models similar to those described above.

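### Section 5.4 collects discharge and 4 to 12 month status only in survivors and has no rule for deaths, so the Aim 3 treatment contrast is conditional on survival although all analysis is called intention-to-treat

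*Combined protocol and SAP*

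**What the plan says.** Specific Aim 3 (section 2.2) sets out to assess the impact of baseline characteristics, "study intervention and other therapies and interventions on" the infant's status at discharge and at the telephone surveys. Section 2.1 also names oxygen need at discharge or day 120 among the safety outcomes that milrinone is hypothesised not to worsen.

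Section 5.4 then says three things:

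- "Among survivors, respiratory and nutritional status at discharge and at 4, 8 and 12 months of age will be collected".
- Longitudinal outcomes, including the 12-month nutritional and pulmonary ones, get models with time, a time-by-treatment interaction and "random effects to account for the correlation between measures taken on the same individual over time". Categorical outcomes get analogous generalized linear models.
- "All analysis will be by intention-to-treat".

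No sentence says how an infant who has died enters these models or the CLD grades in section 3.2 (vii). Other outcomes do have a rule. For the primary outcome, section 3.1 says the last OI or OSI "prior to initiation of ECMO or death will be used for analysis". Section 3.2 has rules for death in the 24 h analysis with an assigned OI, the 48 and 72 h OI, and the inspired-oxygen area under the curve.

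On mortality, section 2.3.1 says of the ventilation trial: "The overall mortality by one year of postnatal age was 27% in this trial". Section 3.5 says: "Infants with CDH represent a high-risk population with mortality ranging from 30 to 40" per cent.

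**The concern.** Whether an infant is alive at discharge or at 12 months is settled after randomisation and may depend on treatment. A comparison restricted to survivors is therefore not the randomised comparison that the intention-to-treat sentence promises. If milrinone keeps alive some very sick infants who would otherwise have died, they join the milrinone survivors and can raise that arm's rates of oxygen and medication use. If milrinone costs lives, the remaining survivors can look healthier than the control survivors. In both cases the contrast can point the wrong way on an outcome that section 2.1 treats as a safety question. The results also feed the design of a definitive trial (section 5.5.3.2).

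**Working it through.** **1. Mortality figures.**

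- Ventilation trial, Table 3: (25 + 21)/(80 + 91) = 46/171 = 26.9%, which reproduces the stated 27%.
- Registry, Table 1: 160/(341 + 160) = 160/501 = 31.9%, which reproduces 32%. Median stay of those who died was 16 days, well before the first call at 4 months.
- Network infants of at least 36 weeks, Table 9: survivors (94 + 101)/(142 + 133) = 195/275, so 80/275 = 29.1% died.
- OI of 10 or more, Tables 6 and 7: 18/57 = 31.6% or 18/58 = 31.0%.

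**2. Expected deaths per arm of 33.** 33 × 0.27 = 8.9; 33 × 0.32 = 10.6; at the upper figure of section 3.5, 33 × 0.40 = 13.2. About 20 to 24 infants per arm would have follow-up values.

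**3. Can the direction reverse?** Assumptions, not in the documents: 30% of infants who would survive in either arm need oxygen, milrinone does not change that, and 80% of infants who survive in one arm only need oxygen. Control mortality is 32%.

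| Milrinone mortality | Oxygen among survivors, control v milrinone | Death or oxygen, all randomised, control v milrinone |
|---|---|---|
| 22% | 30.0% v (0.68 × 0.30 + 0.10 × 0.80)/0.78 = 36.4% | 0.32 + 0.204 = 52.4% v 0.22 + 0.284 = 50.4% |
| 42% | (0.58 × 0.30 + 0.10 × 0.80)/0.68 = 37.4% v 30.0% | 0.32 + 0.254 = 57.4% v 0.42 + 0.174 = 59.4% |

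The survivor contrast has the wrong sign in both rows. This shows direction only; its size comes from the strong 80% assumption.

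**4. Size under a severity model.** Assume a standard normal severity score, oxygen probability logistic(−1 + 1.5 × severity) in both arms, and mortality of 32% v 22%.

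- Death fully determined by severity: oxygen among survivors is 18.3% v 22.1%, a spurious 3.8 points. Alive without oxygen is 0.68 × (1 − 0.183) = 55.6% v 0.78 × (1 − 0.221) = 60.8%.
- Latent correlation of severity with death between 0.3 and 0.7: the spurious difference is 1.0 to 2.5 points. This is the more plausible case, because Table 7 shows measured severity separating deaths only loosely: 8/21 = 38% in severe v 10/37 = 27% in moderate HRF.

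**5. Against the noise.** Survivors number about 33 × 0.68 = 22.4 and 33 × 0.78 = 25.7. The 95% half-width is 1.96 × √(0.183 × 0.817/22.4 + 0.221 × 0.779/25.7) = 0.23, or 23 points. With both rates at 30% and 22 to 24 survivors per arm it is 26 to 27 points. A 3.8-point shift against a standard error of 23/1.96 = 11.7 points moves the chance that milrinone looks worse from 50% to about 63%.

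**The case against.** **Missing data.** A reader might infer that the plan treats death as missing data. It nowhere says so. The survivor sentence describes data collection, and status cannot be recorded for an infant who has died. Most deaths would precede the first call, so the random-effects model would have no values to extrapolate from and would simply compare survivors. Only for an infant who dies between assessments would later values be handled implicitly as missing. The supported statement is that there is no rule for death.

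**Severity adjustment.** The primary model is adjusted for HRF severity, and other continuous outcomes are to be analysed similarly. If the HRF stratum split the same severity variable that drives death and oxygen need (21 of 58 severe, as in Table 7), adjustment would cut the 3.8 points to below 1. That is a best case, since two HRF levels are an imperfect proxy, and the longitudinal sentence does not repeat the adjustment. The point stands in part.

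**Assumed effect on death.** A 10-point fall in mortality alone is generous. The 10-point effect in section 5.1 is for death or ECMO, 40% to 30%. This stands, and is why no size is claimed as an estimate.

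**Deaths are visible.** Survival without ECMO to discharge or day 120 is secondary outcome (viii) and part of Aim 4, and section 5.4 collects mortality. This helps a careful reader but does not change what the Aim 3 contrast estimates.

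**Pilot status.** These are secondary outcomes and no stopping or success rule rests on them. That limits the consequence; it does not justify the intention-to-treat label.

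**Conclusion.** The concern holds. As written, section 5.4 gives a treatment contrast conditional on post-randomisation survival, under an intention-to-treat label, in a population where about 9 to 11 or more of 33 infants per arm are expected to die. If milrinone changes survival, the contrast can be biased either way. If it does not, the bias from this source should be small.

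The documents do not fix the size. Under the severity model it is about 1 to 4 points before HRF adjustment, and less after. Larger values need stronger assumptions, such as most saved infants needing oxygen. All of these are small beside a half-width above 20 points. A reader might infer that the plan will make a life-saving drug appear significantly harmful; the figures do not support that. The realistic risk is that a pilot estimate is read in the wrong direction when the next trial is designed.

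This looks like an omission and not a deliberate choice. The protocol sets rules for death in its short-term oxygenation outcomes, and its own Table 3 lists deaths beside the CLD grades, with rows that account for every infant (37 + 7 + 2 + 9 + 25 = 80; 50 + 13 + 1 + 6 + 21 = 91).

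**What to change.** In section 5.4:

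- Analyse pulmonary status at discharge and at 4, 8 and 12 months, and the CLD grades, in all randomised infants with death as the worst category. Two workable forms are a binary composite of death or use of oxygen or respiratory medication, and a rank-based ordered outcome stratified by HRF severity.
- Do not rely on a proportional-odds model alone. In the 3.8-point illustration the cumulative odds ratios, control v milrinone, are (0.32/0.68)/(0.22/0.78) = 1.67 for death and (0.444/0.556)/(0.392/0.608) = 1.24 for death or oxygen, whereas the model assumes them equal.
- Keep survivor-only comparisons of oxygen, medication, weight, length and head circumference as descriptive. Label them conditional on survival and not intention-to-treat, and show deaths by arm beside them.
- Record a death after discharge as a death, not as a missed call.

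The cost is wording in the analysis plan; section 5.4 already lists mortality among the data collected. The downside is that the composite is partly driven by death, so its components must be reported separately.

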2.3.2. Etiology of Pulmonary Hypertension Associated with CDH

The histological findings of CDH show pulmonary vascular remodeling superimposed on hypoplasia or pruning of the vascular bed associated with structural and functional changes in the heart, airways and lung parenchyma (Gien and Kinsella 2016). Pulmonary hypertension associated with CDH is often severe and resistant to treatment with conventional pulmonary vasodilators such as iNO (1997) (Gien and Kinsella 2016). Poor oxygenation response to iNO and other conventional vasodilators may be secondary to:

Right ventricular dysfunction: Remodeled pulmonary vasculature in CDH results in severe PPHN and leads to RV dysfunction. Milrinone significantly improves RV diastolic function and marginally increases RV systolic velocity in CDH (Patel 2012) resulting in improved pulmonary blood flow and oxygenation. A recent case series from Royal Children's Hospital, Melbourne, Australia demonstrated that right ventricular diastolic dysfunction measured by tissue Doppler on day 1 and 2 of life correlated with length of stay and duration of respiratory support (Moenkemeyer and Patel 2013).

Left ventricular dysfunction: Abnormalities of the left ventricle have been reported in infants with CDH (Siebert, Haas et al. 1984, Schwartz, Vermilion et al. 1994). When compared to neonates with other causes of PPHN, infants with left sided CDH had significantly lower left ventricular mass assessed by echocardiography. Moreover, infants with CDH who required ECMO had a lower left ventricular mass

[figure not shown]

Figure 2. Patients with left sided CDH may have left ventricular hypoplasia and dysfunction. Such dysfunction may be associated with elevated left atrial pressure and pulmonary venous hypertension. Inhaled NO may result in pulmonary arterial dilation and exacerbate pulmonary edema in the presence of pulmonary venous hypertension. Milrinone, by improving left ventricular diastolic and systolic function reduces left atrial pressure and also dilate pulmonary vasculature resulting in improved oxygenation in CDH. The presence of hypoplastic lungs with remodeled pulmonary vasculature and volutrauma, barotrauma and oxygen toxicity contribute to poor response to pulmonary vasodilator therapy. We hypothesize that a combination of milrinone with "gentle" ventilation will improve oxygenation and response to pulmonary vasodilator therapy in CDH.

either by echocardiogram or at post-mortem, than those patients who did not require ECMO (Schwartz, Vermilion et al. 1994),(Siebert, Haas et al. 1984). Reduced left ventricular output has been documented in left sided and right sided CDH (Byrne, Keller et al. 2015). It has been proposed that reduced left ventricular mass contributes to functional LV hypoplasia and results in increased left atrial pressure and pulmonary venous hypertension (Kinsella, Ivy et al. 2005). This helps to explain why iNO and other pulmonary arterial dilators are perhaps less effective in diaphragmatic hernia. These agents can often worsen oxygenation in the presence of pulmonary venous hypertension and/or cardiac dysfunction (figure 2) (Lakshminrusimha 2012) in both children (Baird, Havalad et al. 2012) and adults (Bocchi, Bacal et al. 1994). Administration of an inodilator (an agent with both cardiac inotropic function and vasodilator effect) such as milrinone may improve LV dysfunction (figure 1) (Gien and Kinsella 2016) and promote pulmonary vasodilation and oxygenation (Cai, Su et al. 2008, Cai, Su et al. 2008).

[figure not shown]

Figure 3. "Inodilator" (inotropy + vasodilator) function of milrinone: By inhibiting breakdown of cAMP in cardiac muscle, milrinone acts as an inotropic agent. Similar effect in arterial smooth muscle results in pulmonary (and systemic) vasodilation. Inhaled NO is shown to increase PDE3 activity in animal studies. By acting through cGMP and cAMP, NO and milrinone demonstrate biochemical synergy and enhance pulmonary vasodilation.

Induction of cAMP / cGMP degrading PDE by hyperoxia and iNO: Cyclic GMP and cAMP are important second messengers that promote pulmonary arterial smooth muscle cell relaxation (Figure 3). Their concentration is regulated by specific phosphodiesterases such as the cGMP specific PDE5 and cAMP-specific PDE3. Animal models of PPHN demonstrate increased PDE3 expression, which could promote vascular dysfunction (Murray, MacLean et al. 2002). Recent laboratory studies also indicate that hyperoxic ventilation with iNO dramatically increases PDE3 activity (Chen, Lakshminrusimha et al. 2009), suggesting that these therapies may

reduce cAMP and paradoxically contribute to vascular dysfunction (Thelitz, Oishi et al. 2004). Inhibiting PDE3 by milrinone enhances cAMP levels and promotes vasodilation of pulmonary arterial rings in animal models of PPHN (Lakshminrusimha, Porta et al. 2009) and following hyperoxic ventilation and/or iNO (Chen, Lakshminrusimha et al. 2009) similar to that encountered by many babies with CDH.

